The treatment group: The PATH group will be granted password protected access to one of the 3 PATH levels based on their baseline fitness status. The intervention is designed to help participants increase their baseline PA via health coaching, self-monitoring and pragmatic workout videos that provide convenient options for overcoming socio-environmental barriers to PA. After randomization, the PA coach will work with each participant to develop their PA prescription guided by the FITT-VP principle¹ which recommends the frequency, intensity, time/duration, type, volume and progression of PA regimen. The goal of the exercise prescription will be to increase baseline MVPA by ≥ 60 min/week or 6000 steps/week over the course of the study. Our PA prescription process will begin by identifying a suitable PATH level for each participant based on their estimated maximum rate of oxygen consumption during incremental exercise (VO₂ max).¹ The VO₂ max will be predicted using a validated non-exercise prediction model for peak VO₂ (VO₂ peak) whose covariates include sex, age, waist circumference, resting heart rate and PA index.² Individuals with predicted VO₂ max $\leq 35^{\text{th}}$ percentile rank for their age and gender will be assigned to the Beginner PATH level (includes light intensity PA <3 METs). Those with VO₂ max between 35th and 75th percentile rank will be assigned to Intermediate PATH level which includes moderate intensity PA (3-6 METs) in addition to the Beginner PATH content. Participants with VO₂ max greater than 75th percentile rank will be assigned to Proficient PATH level which includes vigorous intensity PA (>6 METs) in addition to the Intermediate PATH content. After assigning PATH level, the PA coach will guide each participant in selecting their weekly PA goal and will help them plan to start slow with a plan to establish regular exercise frequencies of 3-5 days every week. The coach will also guide participants to select activities with intensity that help them progress along the PA continuum (i.e., sedentary to light PA to MVPA). To foster safety, participants will be instructed to use the Borg Rating of Perceived Exertion (RPE) Scale³ as a guide for adjusting the intensity of their PA regimen. The scale ranges from 6 (no exertion at all) to 20 (maximal exertion) and is embedded with each workout video on PATH. Specifically, the participants will be asked to maintain PA at perceived exertion ratings between 12 to 14 (i.e., moderate level of intensity) on the RPE Scale. To ensure gradual progression in PA intensity, each participant's progress will be reviewed every 2 wks, and more intensity will be allowed, including transition to the next PATH level, when most workouts within the assigned PATH level are perceived to be "very light" (≤ 9 on the RPE Scale). Participants will be requested to rate each workout they engage in on the RPE scale. This method will ensure that the prescribed PA regimen for each individual is based on their physical ability and fitness status. Although the PA coach will provide solid examples of the combination of workout videos that could help participants attain their personalized goals, each participant will have access to all resources within their PATH level and will be encouraged to select a PA regimen that includes their preferred workout videos and other types of PA appropriate for their fitness. The workouts that are recommended by the PA coach and those selected by each participant as favorites will be featured on the personalized PATH dashboard. Box 1 illustrates a PA prescription for Mary, where in the first 2 wks her PA regimen includes her usual walks (40 mins of MVPA/wk or 4000 steps/week) and 10 mins of additional dance workouts each week.

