
Box 1. Mary's PA prescription

Mary is a 45-year old woman with a VO₂ max of 25.1 (5th percentile). She reports 40 mins of MVPA & 4000 steps derived from walking for 20 mins twice/week. Her preference is to ↑ her PA by using dance workout videos. The PA coach will assign Mary to Beginner PATH level based on her VO₂ max, and work with her to develop a plan to ↑ her MVPA by 60 mins/week or 6000 steps/week at the end of study:

- ✓ Gradually increase PA frequency (e.g., an additional day of PA every 4 wks)
- ✓ Set limits for PA intensity: start with workouts that she can do at perceived exertion ratings between 12 to 14. The progress will be reviewed every 2 wks, with more intensity allowed when most workouts within the assigned PATH level are perceived to be "very light" (9 on the RPE Scale).
- ✓ Gradually increase the time. The duration of her PA regimen can be increased by 10 mins of MVPA or 1000 steps every week for the first 6 wks, then maintain.
- ✓ Recommend workout videos with types of PA that align with her goals. The coach will recommend specific workouts that can help Mary attain her goals, but she will have an option to select her favorite workouts at any time.
- ✓ Flexible strategy for attaining desired PA volume. Mary can attain the desired volume of weekly PA by either ↑ her routine walks or via her favorite workouts.
- ✓ Evaluation of progress every 2wks. The PA coach will call Mary twice a month to review and revise the PA prescription based on the progress made. After 6 successful weeks, Mary can focus on maintaining her MVPA at 100 mins/wk or 10,000 steps/wk. She can also continue with the gradual increase in PA volume.

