Measures of adherence and acceptability (Aim 1). Wrist-worn ActiGraph GT9X will be used to measure PA outcomes. Throughout the 12-week Study, participants will be asked to self-monitor their daily PA. The PA tracker will be worn on the wrist for at least 10 hours per day when a participant is awake. The tracker will be connected to the CenterPoint app which will help the study team monitor the participants' progress throughout the study. Two weeks and one week before the end of the study, the study team will send reminders to participants (via text message, email, phone call and push notification) to wear their PA tracker for 7 days before they are scheduled for their end of study assessment. Adherence to PA self-monitoring will be indicated by the number of weeks with ≥ 4 days (3 weekdays and 1 weekend day) of valid wear time (≥ 10 hrs). PATH utilization data will be collected via Web analytics, while a post-intervention survey will assess intervention acceptability.

Measures of PA and cardiometabolic outcomes – administered at baseline and 12 weeks (Aim 2). Body weight (assessed via Fitbit Aria 2 digital scale), waist circumference (assessed via Perfect Waist Tape Measure) and blood pressure (assessed via Omron Model BP7450) assessment will be done by the participant using the equipment shipped to their address by the study, and under the supervision of the study team via HIPAA compliant zoom video conference. The instructions for weighing will include asking participants to wear light clothing and stand bare feet on the scale's footpads. The recorded weight will be available to the study team immediately and via Fitbit API. When taking the blood pressure, the participant will be instructed to apply the cuff

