on the left bare arm, ensuring that nothing is constraining the arm above the cuff. The easy-wrap ComFit cuff used in Omron Model BP7450 fits standard to large adult arms ranging from 9 to 17 inches in circumference.⁶ After applying the cuff, the participant will be asked to relax, sitting in a chair with both feet resting flat on floor and back straight and supported. After resting for at least 5 minutes with the left arm resting comfortably on a flat surface at heart level, the participants will be asked to turn on the BP machine which will be programmed to take 3 measurements at one-minute interval. Any participant with two readings of elevated BP (>130/80) will be referred to their PCP for management. Blood samples for glycated hemoglobin (HbA1c) and lipids (LDL, HDL, and total cholesterol) will be collected via fingerstick using HemaSpot SE kits which will be mailed to participants ahead of baseline assessment. The samples will be mailed to the lab for analysis using established protocols for dry blood spot method. Type 2 diabetes risk score will be calculated using the ADA risk calculator with covariates that include; age, sex, family history of diabetes, history of hypertension, obesity, and PA.¹⁵ **PA measures:** Barriers to exercise self-efficacy will be assessed via BARSE scale,¹⁶ while ActiGraph GT9X will be used to assess participants' PA patterns including steps, light PA and MVPA. These metrics will be calculated using Freedson adult VM3 cut points.¹⁸ For Aim 2, only the 7- day Actigraph data collected during baseline and 12-wks assessments will be used. Since PATH is expected to increase baseline MVPA by ≥ 60 mins or 6000 steps at the end of the study, percent adherence will be calculated as: [(Post-intervention MVPA - Baseline MVPA) / MVPA goal] $\times 100$ (e.g., [(140-90)/60] $\times 100 = 83\%$ (The same formulae will be used for steps). Pre and post-intervention VO_2 max will be calculated using the non-exercise prediction model for VO_2 peak.² described earlier.

Data/Collection Tool	Baseline	3 months
Screening Questionnaires		
Sociodemographic Questionnaire	X	
Medical History Questionnaire	X	
Physical Activity Readiness Questionnaire	X	
American Diabetes Association Risk calculator	X	X
Barriers Self-efficacy Scale	X	X
Paffenbarger Exercise Habits Questionnaire	X	X
PROMIS SF Sleep Disturbance Questionnaire	X	X
PROMIS SF Sleep-Related Impairment Questionnaire	X	X
Automated Self-Administered 24HR Dietary Recall	X	X

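### Does the percent-adherence formula count extra tracker wear as extra physical activity?

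*Protocol*

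**What the plan says.** Under Measures of PA and cardiometabolic outcomes (Aim 2), PA measures, the Protocol defines the score: "percent adherence will be calculated as: [(Post-intervention MVPA - Baseline MVPA) / MVPA goal", times 100. Its example takes 140 and 90 minutes against a goal of 60 and arrives at 83%. For step counts it adds: "The same formulae will be used for steps". The data source is fixed in the same place: "For Aim 2, only the 7- day Actigraph data collected during baseline and 12-wks assessments will be used".

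The denominator is weekly. In the treatment group description: "The goal of the exercise prescription will be to increase baseline MVPA by ≥ 60 min/week or 6000 steps/week".

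The wear provisions stand in the section on adherence and acceptability (Aim 1). The daily instruction is "The PA tracker will be worn on the wrist for at least 10 hours per day when a participant is awake". Adherence to self-monitoring is counted as "the number of weeks with ≥ 4 days (3 weekdays and 1 weekend day) of valid wear time (≥ 10 hrs"). Shortly before study end, participants are reminded through four channels "to wear their PA tracker for 7 days before they are scheduled for their end of study assessment". No matching reminder is described for the baseline window.

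**The concern.** A weekly total depends on how many days the device was on the wrist. The formula has no term for this, and the only valid-wear rule in the document belongs to another measure. Because only the closing window has documented reminders, one could expect more worn days at week 12 than at baseline, and part of the resulting difference would be credited to PATH. The Protocol says its main interest is change within each group, so the control arm would not automatically remove such an artefact.

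Two further worries attach to this one. The step goal seems to be built from exercise walks alone (Box 1: "She reports 40 mins of MVPA & 4000 steps derived from walking for 20 mins twice/week"), whereas the tracker counts every step. And each end of the comparison rests on one week, although the tracker is worn for all 12. If all this held, the score for the 60-minute or 6000-step goal would partly measure wear compliance and week-to-week noise.

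**Working it through.** **Inputs.** From the Protocol: goal 60 min/week or 6000 steps/week; example values 140 and 90 min; 7-day windows at both ends. Assumed, because the Protocol gives no figures: 4 to 7 worn days per window, equal activity on each day, 3000 to 7000 tracker steps a day, and a week-to-week SD of 30 to 90 min.

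**1. The Protocol's own figure.** (140 − 90)/60 = 50/60 = 83.3%. It reproduces.

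**2. If the terms were unadjusted sums.** Recorded total = weekly MVPA × days worn/7.
- Example with 4 worn days at week 12: 140 × 4/7 = 80, so (80 − 90)/60 = −16.7%.
- Example with 4 worn days at baseline: 90 × 4/7 = 51.4, so (140 − 51.4)/60 = 147.6%.
- No true change at 90 min/week, 4 days then 7: (90 − 51.4)/60 = +64.3%. With 7 days then 4: −64.3%.
- No true change, one extra day: (90/7)/60 = 21.4%.
- No true change, 4 days then 7, at 40 min/week: (40 × 3/7)/60 = 28.6%. At 140 min/week: (140 × 3/7)/60 = 100%.
- Equal wear at both ends: 0.

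**3. If the terms are 7 × the mean per valid day.** No true change at 90 min/week, 4 days then 7: baseline 7 × 51.4/4 = 90, week 12 7 × 90/7 = 90, score 0. With full wear at both ends the worked example is still 83.3%. The formula and example therefore cannot tell the two readings apart.

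**4. Steps.** The score is a change against an increment, so habitual steps cancel. At an assumed 5000 a day, baseline is 35,000 a week. Adding 6000 gives 41,000, and (41,000 − 35,000)/6000 = 100%, as intended. One extra recorded day would score 3000/6000 = 50% to 7000/6000 = 117%, but again only with unadjusted sums.

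**5. Single-week noise.** For a participant with no true change, P(score ≥ 100%) = 1 − Φ(60/(SD × √2)): 0.079 at SD 30, 0.240 at SD 60, 0.319 at SD 90. This noise is symmetric about zero and does not bias a group mean. Averaging four weeks at an assumed correlation of 0.6 would reduce the standard error to √((1 + 3 × 0.6)/4) = 0.84 of its single-week value, a modest gain.

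**The case for a change.** The strongest case for a change is that the Protocol is not silent here: it fixes the formula, the example and the data source, and leaves wear out of all three. The reminders are asymmetric as written. The control group description names differential ActiGraph use as something to look at, so equal wear is not taken for granted. The possible artefact can reach the whole goal, and the remedy costs a line.

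What stands is narrow. The formula does not say how a weekly value is obtained when fewer than seven days are valid, and the 4-day, 10-hour rule is not tied to it. The rest does not hold up:
- Reading the terms as unadjusted sums is an inference.
- The direction is open. Baseline is also described as 7-day data, its prompting is simply not described, and the closing reminders may do no more than offset fatigue after 12 weeks of wear.
- The 4-day minimum is borrowed from the self-monitoring measure, so the 4-versus-7 figures show an assumed extreme.
- Differential ActiGraph use is listed as a contrast the control data will inform. It is not stated as expected.
- Box 1 is one illustrative, self-reported case. The scored goal is an increment, and resetting it would be a matter of activity prescription.
- Using the end windows only is a deliberate choice that matches a goal set for the end of the study. Activity is meant to build up over the first six weeks, so an average over all weeks would answer another question.
- Scoring the controls over their first 12 weeks would hold them to a PATH goal they have not been given.

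**Conclusion.** No change follows. The sensitivity is real under one reading: at 90 min/week, 4 against 7 worn days moves the score by 64 percentage points in either direction, and one day by 21. Those sizes rest on unadjusted sums, constant daily activity and an assumed spread of wear. Under the customary reading, a valid-day mean scaled to a week, the artefact is zero on the same assumptions, and the Protocol's formula and example are compatible with it. How accelerometer days become a weekly value is ordinary SAP content, and the SAP is not shown, so its absence from the Protocol is not a defect. The stakes are also limited: this is a feasibility study, and the Protocol does not name percent adherence as a primary outcome or attach a success threshold to it. The step-scale and single-week points are, respectively, removed by the change score and a fair trade-off.

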The PA prescription will be revised after every 2 weeks based on the progress made. Those who manage to increase PA by ≥ 10 minutes each week of MVPA or 1000 steps for 6 consecutive weeks will attain the study goal and their plan for the remaining study period will be to maintain the improved PA regimen. However, the participant can opt to continue with gradual increase in PA volume. To simplify access and support PA maintenance, the workout videos are organized in specific categories (e.g., walking, dance, steps aerobics) and can be sorted by duration and METs. To reduce risk of injury, the amount and intensity of PA will be increased gradually over the course of the study, as advocated by ACSM.⁴ Although there are no established standards on how to increase PA gradually, available evidence suggests that it is safe to increase

MVPA by about 10 minutes or 1000 steps every week.^{4,5} Each participant will be provided near real-time data on their progress towards their weekly and monthly goals on the PATH dashboard. *To complete the PA prescription, participants will provide their preferred schedule for receiving PA reminders and twice a month phone calls from the PA coach to monitor progress and revise PA goals.* Participants will also be given contacts of the PA coach with instructions to reach out if they need help before scheduled calls. During the study period, participants will be encouraged to adhere to their PA goals and share their experiences on the PATH community forum moderated by the study staff. At the end of the study, we will survey participants for feedback on resources that were most helpful to them and ideas for improving the PATH intervention.

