Wait-list control group: Participants in this group will not have access to the PATH intervention until after 12 weeks when they cross over. After randomization, the control group will be provided with a copy of the *Be Active Your Way* booklet, developed by the Centers for Disease Control (CDC) to help individuals integrate PA in their daily lives.⁶ The key strategies used in the booklet are outlined in Box 2. We have chosen this control strategy to mirror usual care where patients are provided with self-help handouts. The *Be Active Your Way* booklet was selected because it is evidence based, free to download and recommended by the CDC as a pragmatic self-help resource for promoting PA.⁶ In addition, the control group will receive bi-weekly newsletters focusing on general health. The control group data will help contrast the important aspects of our study, including differential ActiGraph use and retention rates between the control and intervention groups, as well as the trend in PA and cardiometabolic risk changes. After 12 weeks, the outcome assessments will be done, and the control group will be given access to the PATH intervention. Once given access to PATH, participants will be subject to all the study procedures described for the treatment group. No follow-up is planned after the post-intervention assessments for both the intervention and control groups.

Box 2. Be Active Your Way get started plan

- ✓ **Goal:** Build up your PA routine overtime.
- ✓ **Start by doing what you can** & then look for ways to do more. If you have not been active for a while, start out slowly. After several wks or months, build up your activities, then do them longer & more often.
- ✓ **Walking is one way to add PA to your life.** When you first start, walk for 10 mins a day on a few days during the first couple of weeks.
- ✓ **Add more time and days.** Walk a little longer. Try 15 min instead of 10 mins. Then walk on more days/wk.
- ✓ **Pick up the pace.** Once this is easy to do, try walking faster. Keep up your brisk walking for a couple of months. You might add biking on weekends for variety.

Expected results, potential pitfalls and solutions: Although

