a wait-list control design may artificially inflate the intervention effects in an efficacy trial,⁷ our feasibility study primary focus is on within-group changes. Therefore, a wait-list strategy may enhance retention and help control for passage of time and assessments⁸ without impacting study outcomes. Another potential pitfall is recruitment. However, based on our experiences, we do not anticipate significant difficulties recruiting women, but more proactive strategies will be needed to recruit men and minorities. To address the challenge, we have built relationships with strategic community stakeholders such as barbershops where men frequent, and the CTSI Community PARTners core which specializes on recruiting minorities. In addition, the remote nature of the intervention is likely to make the study appealing to men and other underserved populations with low participation in biomedical research. These strategies will help us attain our recruitment targets. To foster safety, our exclusion criteria will help exclude individuals who are unfit to engage in unsupervised PA. Moreover, the PA prescriptions will be personalized according to ability and preference. All participants will be educated on PA safety using ACSM Guidelines⁴ and will be given non-slip exercise mats.

Screening assessments – Questionnaires will be used to assess barriers to exercise self-efficacy, PA readiness, medical history and risk of diabetes, PA habits, sleep patterns, depressive symptomatology, diet, fatigue, and stress. Table 1 outlines the specific data collection instruments and their timeline. These data will be used to evaluate eligibility and to describe lifestyle and other cardiometabolic factors typically related to PA.

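### Wait-list controls start PATH after 12 weeks with no stated re-check of exercise readiness: a minor, cheap safety improvement

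*Protocol*

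**What the plan says.** Table 1 has two assessment columns, Baseline and 3 months. The row "Physical Activity Readiness Questionnaire" is marked at Baseline only, and so is the Medical History Questionnaire. Under Screening assessments the protocol gives the purpose of the questionnaires: "These data will be used to evaluate eligibility and to describe lifestyle and other cardiometabolic factors typically related to PA". Under Expected results, potential pitfalls and solutions it relies on entry screening for safety: "our exclusion criteria will help exclude individuals who are unfit to engage in unsupervised PA".

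For the wait-list control group the order of events is stated in two sentences: "After 12 weeks, the outcome assessments will be done, and the control group will be given access to the PATH intervention", and then "Once given access to PATH, participants will be subject to all the study procedures described for the treatment group".

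Other protections are described. Blood pressure is taken at both time points, and two elevated readings lead to referral to the primary care provider. The coach builds the prescription with the participant, effort is held at 12 to 14 on the RPE scale, and volume rises gradually. There is safety education ("All participants will be educated on PA safety using ACSM Guidelines"), there are "twice a month phone calls from the PA coach to monitor progress and revise PA goals", and between calls "Participants will also be given contacts of the PA coach with instructions to reach out if they need help before scheduled calls".

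**The concern.** Randomization and both forms sit in the Baseline column, and the intervention arm receives PATH after randomization, so its readiness screen is current when its programme starts. Controls start the same programme about 12 weeks later on the same screen. The schedule therefore fits the start of exercise in one arm and not in the other.

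At stake is participant safety rather than inference. A control who develops chest symptoms, a joint injury or a new diagnosis during the wait could begin a largely unsupervised programme without having been asked about it.

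**Working it through.** The plan gives no figure to reproduce on this point. The check is a reading of the schedule against the crossover text, plus a simple sum for early exposure.

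**1. Count of Table 1, Screening Questionnaires.**
- Rows: 14.
- Baseline only: 3 (sociodemographic, medical history, physical activity readiness).
- Repeated at 3 months: 14 − 3 = 11 (ADA risk calculator, barriers self-efficacy, Paffenbarger, two PROMIS sleep forms, dietary recall, depression scale, perceived stress, fatigue scale, physical activity index, MAQ).
- Readiness or medical history forms, by name, among the 11 repeated: 0.

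**2. Does any repeated item do the job under another name?**
- Blood pressure: detects elevated pressure only. Referral is not stated as a condition for access.
- ADA calculator: includes history of hypertension, but its stated use is a diabetes risk score.
- Fatigue, depression, stress and sleep scales: cover some symptoms, but are not described as a check for injury, new diagnosis or a reason not to exercise.
- Predicted VO₂ peak: built from age, waist circumference, resting heart rate and activity index, by sex. It could update the PATH level but cannot show a new injury or symptom.

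**3. Do the treatment-group procedures supply the question?** They apply once access has been given. As described, they are level assignment, prescription with the coach, RPE guidance, two-weekly review and calls. The stated purpose of the calls is progress and goals, and contact between calls is left to the participant. No readiness or symptom question is described among them.

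**4. Early exposure.** The section on the PA prescription gives steps of about 10 minutes of MVPA per week, each week. Planned increase over baseline in week w = 10 × w min/week, for w up to 6:
- week 1: 10 × 1 = 10
- week 2: 10 × 2 = 20
- week 6: 10 × 6 = 60, which agrees with the protocol's goal of at least 60 min/week.

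The worked example in the protocol is gentler: its participant adds 10 minutes of dance per week in the first two weeks. Before the first two-weekly review, then, the planned increase is about 10 to 20 min/week.

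**The case against.** The strongest reply is that text and table agree with each other: these are screening forms, they are scheduled at screening, and a baseline screen may still be good at 12 weeks. The intervention arm also exercises through week 12 on one baseline screen, and controls are already encouraged by their booklet to build up walking. Existing steps cover much of the risk, and the document shows neither the exclusion criteria nor the rule for a positive readiness answer, so a re-check written elsewhere cannot be ruled out.

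Much of this stands. It limits the point to a small improvement. It does not remove it. The intervention arm is screened when its programme begins and then has regular coach contact. During the wait, controls are described as having a booklet and newsletters, and then start the coached programme. The two places that govern crossover, Table 1 and the wait-list section, are both shown, and neither contains the question.

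A reader might infer more than the document supports:
- *That a 12-week-old screen is invalid.* The protocol gives no validity period for the form.
- *That controls cross over with no safeguard.* Several safeguards are described, and blood pressure is re-measured before access.
- *That Table 1 rules out a re-check.* It has no arm-specific marks and no column for the controls' own PATH course. It shows only that the two forms are not part of the 12-week assessment.

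**Conclusion.** The point holds as a minor safety improvement. As written, wait-list controls move from the 12-week assessments to PATH with no stated re-check of exercise readiness. It applies to every control who crosses over. The number with a new relevant condition cannot be derived from the document, and the planned early increase is modest, so the benefit is real but small and unquantified.

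A reader might also infer that the trial's results are compromised. They are not: the 12-week outcome data are collected before access, so the randomized comparison is untouched.

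The conclusion assumes that no re-check is specified in material not shown, such as the full eligibility criteria, and that the coach's first contact with a crossing control follows only what the protocol describes.

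**What to change.** For the wait-list arm only, after the 12-week outcome data are collected and before PATH access:
- repeat the readiness questionnaire, with one short question on any new symptom, injury or diagnosis since baseline;
- handle any new positive answer by the same rule used at baseline entry, with access deferred until the participant is cleared;
- keep all 12-week data whatever the answer;
- mark the step in Table 1 with a footnote (wait-list arm, before PATH access) and add one sentence to the wait-list section.

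The inactivity and other entry criteria need not be re-applied, so a control who merely became more active during the wait is not held back.

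The cost is one existing form and a brief update at an assessment that already takes place. The downside is that a few crossovers may be delayed. The authors will have to state the baseline rule for a positive answer, or point to it, because the document at hand does not show it.
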